13 STATISTICAL CONSIDERATIONS

13.1 Study Design

This is a phase 1 study of AR-42 in combination with pazopanib in patients with advanced RCC or STS. A modified 3+3 dose-escalation design will be conducted. Additional patients will be enrolled at the MTD until a total of 12 patients have been treated at the MTD.

13.2 Sample Size/Accrual Rates

With the 7 proposed dose levels (-1, 1, 2, 3A, 3B, 4A, and 4B) and starting at dose level 1 (as indicated in Table 1 in Section 6.6), the number of patients needed for evaluation of DLT ranges from 4 to 36. To take into account the up to 20% of patients subsequently found to be inevaluable for DLT, the maximum number of patients required to determine the MTD is 45. Per the dose-escalation plan, it is likely that 4-5 dose levels will be explored. With an average of 4.5 patients per cohort, the likely scenarios involve 18-23 patients and, therefore, it is expected that 23-29 patients evaluable for DLT will be enrolled in the study. With 6 additional patients who will be treated at the MTD, the maximum number of patients needed for the study is 51 with a likely sample size of 29-35 patients.

Based on past recruitments, the recruitment rate is expected to be about 1-2 per month. Therefore, the anticipated enrollment period is expected to be about 15-35 months.

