3 STUDY DESIGN

3.1 General Description

This study is a single-arm, open-label, phase 1 trial to determine the RP2Ds of AR-42 and pazopanib when given in combination to patients with advanced RCC or STS. Eligible patients will have recurrent, unresectable, or metastatic RCC or STS for which pazopanib is an appropriate therapy.

AR-42 will be taken orally once per day on 3 non-consecutive days each week during the first 3 weeks of each 4-week cycle. Pazopanib will be taken by mouth once daily continuously during each cycle.

A modified 3+3 dose-escalation design will be followed until the maximum tolerated doses (MTDs) have been determined. Additional patients will be enrolled until a total of 12 patients have been treated at the MTDs. The maximum number of patients needed is 51 with an expected sample size of 29-35 patients enrolled over a period of about 15-35 months.

Correlative studies will be conducted using samples of tumor that were archived following the most recent surgery or biopsy.

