6.7.3 MTD

Dose escalation will follow a modified 3+3 plan (Table 3) using the dose levels listed in Table 1 and the guidelines in Table 2 to determine the MTDs and the RP2Ds for AR-42 and pazopanib. DLT is defined in Section 6.7.2. Patients will be enrolled in cohorts of 3 beginning at dose level 1.

Table 3. Modified 3+3 Dose Escalation		
Number of Patients with DLT at a Given Dose Level (Refer to Section 6.7.2 for DLT definition)	Escalation Decision Rule (Refer to Table 1 in Section 6.6 for dose levels and Table 2 for dose-escalation guidelines)	
0 out of 3	Enroll 3 patients at the next dose level.	
≥ 2 ^A	MTD has been exceeded. No further treatment at this dose is allowed. Three (3) additional patients will be enrolled per dose levels as noted on Table 2 .	
1 out of 3 ^A	Enroll at least 3 more patients at this dose level.	
	 If 0 of these 3 patients experience DLT, escalate doses to the next dose level (unless MTD has already been exceeded at that dose level, in which case, the current dose level is the MTD).^B 	
	• If 1 or more of this group experience DLT (total of 2), then the MTD has been exceeded. Three (3) additional patients will be enrolled at the next lower dose level if only 3 patients were treated previously at that dose. ^B	
Patients enrolled to complete a total enrollment of 12 at the MTD		
≤ 3	The MTD has been confirmed. ^B	
≥ 4	The MTD has been exceeded; 3 additional patients will be enrolled at the next lower dose level (if available). ^B	
	3 PPE at any dose level will NOT be considered a DLT. grade 3 PPE will be considered DLT.)	
 B. Confirmation that a dose level does not exceed the MTD requires evaluation of a minimum of 6 DLT-evaluable patients. To confirm the RP2Ds, additional patients will be enrolled at the MTDs until a total of 12 patients have been treated at the MTDs. 		

 Table 3. Modified 3+3 Dose Escalation

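### The maximum of 51 patients in sections 3.1 and 13.2 assumes that no expansion fails, and the 23-29 patients that 13.2 calls DLT-evaluable are enrolled numbers

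*Combined protocol and SAP*

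**What the plan says.** Section 13.2 builds the sample size in steps. With seven dose levels and a start at level 1, "the number of patients needed for evaluation of DLT ranges from 4 to 36". After an allowance for up to 20% of patients being inevaluable for DLT, "the maximum number of patients required to determine the MTD is 45". Six further patients at the MTD are then added, and "the maximum number of patients needed for the study is 51 with a likely sample size of 29-35 patients". Section 3.1 repeats it without conditions: "The maximum number of patients needed is 51".

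For the expected size, 13.2 takes 4-5 levels at an average of 4.5 patients, so that "the likely scenarios involve 18-23 patients", and continues that "it is expected that 23-29 patients evaluable for DLT will be enrolled in the study".

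Table 3 in section 6.7.3 governs the stage in which the MTD is filled to 12 patients. With 3 or fewer DLTs the MTD is confirmed. With 4 or more, "The MTD has been exceeded; 3 additional patients will be enrolled at the next lower dose level (if available"). Note B to the table requires at least 6 DLT-evaluable patients to confirm a level and 12 treated at the MTD. For the earlier stage, when a second DLT appears in a level filled to 6, Table 3 says "Three (3) additional patients will be enrolled at the next lower dose level if only 3 patients were treated previously at that dose".

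**The concern.** A figure given as the maximum should hold for every path that the protocol's own rules allow. Section 13.2 counts one expansion of 6 and assumes that it succeeds. Table 3 provides for an expansion that fails, after which a lower level may have to be opened or filled, confirmed at 6 and taken to 12. Someone who budgets drug supply, approvals or accrual from section 3.1 would take 51 as a ceiling that the escalation rules do not enforce. Neither section states the assumptions behind 51 or says what follows if it is passed.

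The label on 23-29 is a separate slip. These numbers already contain the allowance for inevaluable patients, so calling them evaluable overstates the expected amount of DLT information by the factor 1/0.8.

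**Working it through.** 1. **Inputs.** At most 36 DLT-evaluable patients, 20% inevaluable, 6 further patients at the MTD, 4-5 levels at 4.5 patients each (all section 13.2). Minimum of 6 evaluable to confirm a level, 12 treated at the MTD, and descent with 4 or more DLTs (Table 3 and its note B). Section 13.2 does not derive the 36; it equals six levels of 6. I take the count of 4 or more to cover all 12 patients at the level.

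2. **The plan's figures reproduce.** Enrolled = evaluable/(1 − 0.20).
   - Maximum: 36/0.8 = 45; 45 + 6 = 51.
   - Likely: 4 × 4.5 = 18 and 5 × 4.5 = 22.5, rounded to 23. Then 18/0.8 = 22.5, rounded to 23, and 23/0.8 = 28.75, rounded to 29. Adding 6 gives 29-35.

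   So 51 contains exactly one expansion of 6, and 23-29 is the enrolled count that corresponds to 18-23 evaluable.

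3. **Two paths with one failed expansion.** They use different readings of where 3B stands.

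| Path | Evaluable patients |
|---|---|
| A: levels 1, 2, 3A and 4A at 6 each, 4A not tolerated; 4B passes at 6 and fails at 12; unused 3B is the next lower level and is taken to 12 | 24 + 12 + 12 = 48 |
| B: 4A and 4B fail at 6; 3A passes at 6 and fails at 12; levels 2 and 1 are filled to 6 and fail; level -1 is taken to 12; 3B stays closed | 6 + 6 + 12 + 6 + 6 + 12 = 48 |

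   Each path has six levels of 6 plus two expansions of 6. By 13.2's method, which does not inflate expansion patients, this is 36/0.8 + 12 = 57. Path A needs 3B to be the next level below 4B, and path B needs 3B to stay closed. So 51 can be passed on either reading.

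4. **A failed expansion does not always pass 51.** If five levels hold 6 each (30), the expansion fails (+6), and the next lower level already holds 6 and succeeds at 12 (+6), the total is 42 evaluable: 30/0.8 = 37.5, rounded to 38, and 38 + 12 = 50.

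5. **Chance of a failed expansion.** The documents give no DLT rate, so a range is assumed. For a true rate p at a level that passed with 0-1 DLTs in 6, the chance of 4 or more in 12 is [P(X=0)·P(Y≥4) + P(X=1)·P(Y≥3)] / P(X≤1), where X and Y are independent binomial(6, p). For p = 0.20: (0.2621 × 0.0170 + 0.3932 × 0.0989)/0.6554 = 0.066.

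| Assumed p | 15% | 20% | 25% | 30% | 33% |
|---|---|---|---|---|---|
| Chance of failed expansion | 3% | 7% | 13% | 20% | 26% |

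   These are not chances of passing 51, which are much smaller. Simulating Tables 2 and 3 under six assumed DLT curves (rates of 5-45% across levels, both readings of 3B) gave more than 42 evaluable patients in about 0.1-2.3% of trials. Only the order of magnitude should be taken from this.

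**The case against.** The strongest reply is that nothing depends on 51. The MTD and RP2D follow from section 6.7; no decision rule, estimate or assignment uses the total; and passing it is rare under any plausible DLT curve. That stands, and it is why the point is minor. It does not make an unconditional maximum correct when the protocol's own table can exceed it.

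A reader might infer more than the documents support:

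- **That 57, or 60 with full replacement (48/0.8), is the true maximum.** Table 3 does not limit the number of failed expansions and does not define the next lower level on a two-drug grid. If 3B can open during de-escalation, one failed expansion can reach 42 + 12 = 54 evaluable, or 53 + 12 = 65 enrolled (54/0.8 = 67.5, rounded to 68, if all are inflated).
- **That 51 is passed even without a failed expansion.** Seven levels of 6 would give 42/0.8 = 52.5, rounded to 53, plus 6 = 59. This needs Table 2's step from 3A to 3B, in a table of escalation guidelines, to apply also after 4A and 4B have failed. Table 2's own rule after 4B is to take the highest level without 2 or more DLTs, and Table 3's descent rule refers to a level where only 3 were treated. Read together, these point to 3B staying closed, and full back-fill then gives exactly 51.
- **That adding the last 6 without inflation is an error.** The target is 12 patients treated, not 12 DLT-evaluable, so adding 6 is consistent. The replacement note in 13.6.1 makes another reading possible, but the effect is 1-2 patients.

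**Conclusion.** The point holds as a minor correction. The 51 in sections 3.1 and 13.2 is a planning figure that assumes at most 36 DLT-evaluable patients before expansion, 20% inevaluable and no failed expansion; it is not a maximum. With one failed expansion, two valid paths reach 48 evaluable, or 57 enrolled by 13.2's method. This assumes that the threshold of 4 or more DLTs counts all 12 patients and, for each path, the stated reading of 3B. Passing 51 is unlikely, 51 is not a stopping rule, and the likely size of 29-35 is not shown to be wrong. The label on 23-29 is wrong as written, whatever the reading of the tables.

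**What to change.** - In 3.1 and 13.2, restate 51 as *a planning figure that assumes at most 36 DLT-evaluable patients before expansion, 20% inevaluable and no failed expansion*, and add that a failed expansion under Table 3 can take enrolment above it.
- Reconcile Tables 2 and 3 on what the next lower dose level means and on whether 3B can open during de-escalation. Which rule applies is for the sponsor to decide. Until then, put no other maximum in the text, and no single figure for one failed expansion.
- In 13.2, write *18-23 DLT-evaluable patients, 23-29 enrolled*.
- Optionally, state whether DLT-inevaluable patients among the last 6 are replaced under 13.6.1. If so, the planning figure is 42/0.8 = 52.5, rounded to 53, and the likely size is (18 + 6)/0.8 = 30 to (23 + 6)/0.8 = 36.25, rounded to 37. If not, 51 and 29-35 stand.

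The cost is a few words in two sections and one reconciling line for the tables. No patients are added unless the sponsor chooses replacement among the last 6, which adds about 1-2.

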13.3 Statistical Analysis for Primary Objective

Patients' treatment dose level, dose modification, evaluability for DLT, and DLTs will be listed and summarized by basic descriptive statistics such as frequency and proportion. The MTDs/RP2Ds will be found based on the criteria defined in Section 6.7

13.4 Statistical Analysis for Secondary Objectives

Patients' demographics, AEs and SAEs, treatment status, number of patients who had discontinuation of study therapy, and clinical response will be listed and summary descriptive statistics, including frequency/proportion for discrete variables and mean/median/standard deviation for continuous variables, will be calculated. The clinical response (CR + PR) rate will also be calculated along with its 95% confidence interval.

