1.2.1 Pazopanib in RCC

In RCC, systemic treatment for many patients who have metastatic disease involves drugs targeting angiogenesis. High-dose interleukin 2 in the front-line setting is still recommended for patients with Karnofsky performance status of > 80%, and other immune-based therapies with immune checkpoint inhibitors are showing promise. However, agents targeting angiogenesis remain a cornerstone in the management of this disease. Two different approaches have demonstrated clinical activity in blocking the VEGF pathway. Clinical anticancer activity has been observed with small molecule tyrosine kinase inhibitors (TKIs) (eg, pazopanib, sunitinib, sorafenib, and axitinib) which block the intracellular domain of the VEGF receptor, as well as the monoclonal antibody bevacizumab which can bind circulating VEGF and prevent activation of the VEGF receptor. Among the TKIs, pazopanib and sunitinib are accepted first-line treatment options ($\underline{7}$).

In a randomized phase 3 study of pazopanib versus sunitinib in 1,110 previously untreated patients with advanced RCC, partial responses were observed in 170 patients in the pazopanib group (31%), and one patient had a complete response ($\underline{7}$). The median progression-free survival was 8.4 months with pazopanib (95% confidence interval [CI], 8.3 to 10.9), and the median duration of treatment was 8.0 months (range, 0 to 40) in the pazopanib group. Regarding tolerability, 44% of patients treated with pazopanib had a dose interruption of 7 days or more and 44% of patients had a reduction in the dose. The proportion of patients who discontinued the study drug because of adverse events was 24%. These data demonstrate a favorable pazopanib safety profile compared to sunitinib, with similar efficacy. The results of this study established pazopanib as an acceptable front-line choice in the treatment of RCC with TKI-based therapy.

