1.2.2 Pazopanib in STS

The interaction between VEGF and its receptors involved in angiogenesis plays a role in STS tumor progression and prognosis ($\underline{8}$). Two studies found that high VEGF serum levels correlated strongly with the most poorly differentiated STS ($\underline{9}$, $\underline{10}$).

The randomized multicenter phase 3 "PALETTE" study evaluated pazopanib compared to placebo in 369 patients with STS that had progressed following front-line therapy (11). In this study, the best overall response for patients taking pazopanib was a partial response in 14 of 246 (6%), stable disease in 164 (67%), and progressive disease in 57 (23%). Median progression-free survival was 4.6 months (95% CI 3.7-4.8) for pazopanib compared to 1.6 months (95% CI 0.9-1.8) for patients who received placebo, and median overall survival was 12.5 months (10.6-14.8) compared to 10.7 months (8.7-12.8) for the placebo arm.

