2.2 Secondary Objectives

- 2.2.1 To evaluate the safety and toxicity of AR-42 and pazopanib when given in combination
- 2.2.2 To explore the antitumor effects of the AR-42 and pazopanib treatment regimen in patients with advanced RCC or STS

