4 PATIENT SELECTION

4.1 Inclusion Criteria

A patient must meet all of the following inclusion criteria to be eligible for this study.

- 4.1.1 Recurrent, unresectable, or metastatic RCC or STS (any histologic type) for which pazopanib is an appropriate therapy
- 4.1.2 Measurable or evaluable disease by RECIST v1.1
- 4.1.3 Age \geq 18 years
- 4.1.4 Eastern Cooperative Oncology Group (ECOG) performance status of 0 or 1 (see Appendix 1)
- 4.1.5 Adequate bone marrow function as defined below:
 - Absolute neutrophil count (ANC) ≥ 1200/mm³
 - Platelets \geq 120,000/mm³
 - Hemoglobin ≥ 9.5 g/dL

- 4.1.6 Adequate renal function as defined below:
 - Creatinine ≤ 1.5 x upper limit of normal (ULN) for the laboratory or calculated or actual creatinine clearance ≥ 60 mL/min (see Appendix 2 for the Cockcroft-Gault formula for calculating creatinine clearance)
 - Proteinuria ≤ 2+ [100 mg/dL]) using a random urine sample or < 3.0 gm using a 24-hour sample)

Note: If urine sample indicates $\ge 2+$ [100 mg/dL]), a 24-hour urine sample must be collected and tested; urine protein in the 24-hour sample must be < 3.0 gm/24 hours.

- 4.1.7 Adequate hepatic function as defined below:
 - Total bilirubin $\leq 1.5 \text{ x}$ ULN for the laboratory

Note: Patients with known Gilbert's Syndrome are **not** eligible for this study (Section 4.2.10).

- Aspartate aminotransferase (AST) ≤ 2.5 x ULN for the laboratory
- Alanine aminotransferase (ALT) $\leq 2.5 \times \text{ULN}$ for the laboratory
- 4.1.8 Non-hematologic toxicities from previous cancer therapies resolved to \leq grade 1
- 4.1.9 International normalized ratio (INR) \leq 1.5
- 4.1.10 Activated partial thromboplastin time (aPTT) \leq 1.5 x ULN for the laboratory
- 4.1.11 Left ventricular ejection fraction (LVEF) assessment (eg, echocardiogram, MUGA scan, first-pass technique) performed within 3 months prior to initiation of study treatment indicates an LVEF of ≥ 50%
- 4.1.12 A woman of childbearing potential (WCBP), defined as a woman who is < 60 years of age and has not had a hysterectomy, must have a documented negative serum pregnancy test within 7 days prior to initiating study treatment
- 4.1.13 A WCBP and a male patient with a partner who is a WCBP must agree to use a medically accepted method for preventing pregnancy for the duration of study treatment and for 2 months following completion of study treatment
- 4.1.14 Ability to understand and willingness to sign the consent form

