13.6.3 Efficacy-Evaluable Population

Efficacy-evaluable patients are those who have received any doses of AR-42 and pazopanib in cycle 2 (regardless of the number of doses taken during cycle 1), and have had at least 1 imaging assessment of response after receiving study treatment.

For efficacy evaluation, patients are coded as having a response or not having a response as follows:

- Responders: Best response assessment is a PR or a CR (Section 10).
- Non-Responders: Best response assessment is stable disease or progressive disease; also included are patients who did not have assessment of tumor response at least once after initiation of study treatment or who were otherwise not evaluable for response.

The coding of patients as responders or non-responders will be made by the Sponsor-Investigator with the concurrence of the Biostatistician.

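### Section 13.4 plans one CR+PR rate for RCC and STS combined, with no result by tumor type and no fixed mix of the two diseases

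*Combined protocol and SAP*

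**What the plan says.** The efficacy objective in section 2.2 is "To explore the antitumor effects of the AR-42 and pazopanib treatment regimen in patients with advanced RCC or STS". For its analysis, section 13.4 states that "The clinical response (CR + PR) rate will also be calculated along with its 95% confidence interval". Section 13.6.3 defines one efficacy population and one responder rule, "Best response assessment is a PR or a CR", for all patients.

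Section 4.1 admits "Recurrent, unresectable, or metastatic RCC or STS (any histologic type) for which pazopanib is an appropriate therapy". Neither this criterion, nor section 3.1, nor the sample-size text in 13.2 sets a quota, cap or stratum for either disease. No section of the available text calls for response by tumor type. Section 13.4 does have clinical response listed, so a split is not ruled out, but none is planned.

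Section 1.2.1 reports partial response to pazopanib in 170 patients (31%), plus one complete response, in a phase 3 study of untreated advanced RCC. Section 1.2.2 reports 14 of 246 (6%) in "patients with STS that had progressed following front-line therapy".

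Section 13.5 plans ordinal and logistic models of response on each marker with a 0.05 screen. It names neither a tumor-type term nor the test.

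**The concern.** A response rate over two diseases with very different background rates has no fixed reference value: what to expect from pazopanib alone depends on who happens to enroll. More seriously, the same combined count can come from results that point in opposite directions in the two diseases. The planned statistic would then describe neither of the diseases named in the objective, and an early signal in one of them could go unseen or be reported only as a split chosen after the data were known.

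A secondary, conditional worry concerns 13.5. If a protein is expressed differently in RCC and STS and the two respond at different rates, an unadjusted marker model can flag tumor type rather than the marker.

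**Working it through.** **Plan's own figures.** Section 13.2 reproduces. 4.5 × 4 = 18 and 4.5 × 5 = 22.5, rounded to 23. Allowing for 20% inevaluable, 18/0.8 = 22.5, rounded to 23, and 23/0.8 = 28.75, rounded to 29. Adding 6 gives 29 to 35. The maximum is 36/0.8 + 6 = 51. For STS, 14/246 = 5.7%, stated as 6%. The size of the RCC pazopanib arm is not given, but 170 patients at 31% implies about 540 to 557, consistent with half of 1,110.

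**Expected combined rate with no AR-42 effect.** With RCC share r (not in the documents, so shown over a range) and RCC rate p, the rate is p·r + 0.06(1 − r). RCC rates of 20% and 12% are assumptions, included because this trial does not require untreated RCC.

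| RCC rate | r = 25% | r = 50% | r = 75% |
|---|---|---|---|
| 31% | 12.3% | 18.5% | 24.8% |
| 20% (assumed) | 9.5% | 13.0% | 16.5% |
| 12% (assumed) | 7.5% | 9.0% | 10.5% |

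Over the full range of r at 31%, the rate runs from 6% to 31%. For scale, the sampling half-width 1.96·√(p(1 − p)/n), using the first row, is 11.4, 13.5 and 15.0 points at n = 32 and 13.1, 15.5 and 17.3 points at n = 24. So the mix effect is smaller than sampling error.

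**Masking.** Take 16 RCC and 16 STS (32 is the middle of 29 to 35; the split is assumed). Background predicts 16 × 0.31 + 16 × 0.06 = 4.96 + 0.96 = 5.92 responders, so about 6/32 = 18.8% (Clopper-Pearson 95% CI 7.2-36.4%). The same 6/32 also arises from:

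- RCC 1/16 = 6% (0.2-30.2%)
- STS 5/16 = 31% (11.0-58.7%)

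If the true STS rate were 6%, P(X ≥ 5 of 16) = 0.0019. The planned line is identical in both cases.

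Similarly, 7/35 = 20% (8.4-36.9%) excludes 6% (P(X ≥ 7) = 0.004) but not 31% (P(X ≤ 7) = 0.11). It sits close to what an even mix would give on pazopanib alone (18.5%).

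**Marker screen (conditional).** This was simulated at 16:16 with an STS rate of 6%, a normal marker whose mean is shifted in RCC by the stated number of SDs, and no marker effect within either disease. There were 4,000 trials per cell, with Monte Carlo error of about 0.2 to 0.6 points. The documents give no expression data, so the shifts are assumptions. False-positive rates of the unadjusted logistic model at 0.05:

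| RCC rate | Test | 0 SD | 0.5 SD | 1.0 SD | 1.5 SD |
|---|---|---|---|---|---|
| 31% | Likelihood ratio | 5.8% | 8.6% | 14.4% | 21.0% |
| 31% | Wald | 2.4% | 4.4% | 7.8% | 12.4% |
| 20% | Likelihood ratio | 6.6% | 7.1% | 9.0% | 12.3% |
| 20% | Wald | 2.0% | 2.4% | 3.2% | 4.6% |
| 12% | Likelihood ratio | 6.8% | 7.0% | 8.0% | 8.4% |
| 12% | Wald | 1.2% | 1.3% | 1.4% | 1.6% |

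The excess over 5% at zero shift is small-sample error of the test, not tumor type. The ordinal model behaves similarly (800 trials per cell, likelihood ratio, error about 1 point). Over the same shifts it gives 7.9/7.8/13.2/17.2% with RCC PR 31% and PD 15%, 7.1/7.1/8.1/12.1% with PR 31% and PD 24%, and 6.6/5.6/7.1/7.1% with PR 20% and PD 24%. The RCC progression shares are assumed.

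**The case against.** The strongest reply is that this is phase 1 dose finding. Response is explored, not tested: no null rate, power statement or go/no-go rule rests on it. Section 13.4 is silent on grouping rather than insisting on a combined figure, response is listed anyway, and tumor type is known for every patient, so the split can be made at any time. The mix effect is smaller than sampling error. The 31% comes from untreated RCC, whereas this trial excludes only earlier pazopanib. The 1/16 and 5/16 example is extreme: at background rates its two parts have probabilities of about 2.2% and 0.2%, or about 0.004% jointly. It also treats about 32 patients as evaluable, although 13.6.3 requires dosing in cycle 2 and at least one scan. Rates by disease would still pool dose levels and many STS histologies. The marker argument needs both a large response gap and an expression difference for which there are no data, and 13.5 already says that the study is underpowered.

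All of this is fair as to weight, and it keeps the point modest. It does not remove it. The example shows what the planned summary cannot distinguish, not what is likely, and it needs no RCC benchmark to do so. A split written in advance is better evidence than one chosen after a striking subgroup is seen. The objection to the marker part largely stands, so that part is optional.

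**Conclusion.** The concern holds. The plan gives one response rate with one interval for two diseases whose background rates, by the protocol's own account, are 31% and 6%, with no control of the mix and no planned result by disease. The expected combined rate without any AR-42 effect moves by 12.5 points (24.8% − 12.3% before rounding: 24.75 − 12.25) between 25% and 75% RCC if the 31% applies, by 7 points if the RCC rate is 20%, and by 3 points if it is 12%. Independently of that shift, opposite results in the two diseases can give the same planned line.

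The consequence is limited to secondary and exploratory outputs; the dose-finding objective is unaffected. This is a worthwhile, cheap improvement rather than a flaw in a stated figure. The marker inflation is material only when the response gap is near 31% against 6% and expression differs by about 1 SD or more. With a smaller gap there is little or none.

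**What to change.** In section 13.4, add wording such as:

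> CR+PR will be reported with exact (Clopper-Pearson) 95% confidence intervals separately for RCC and STS. The combined rate is a descriptive line that gives the number of patients of each tumor type.

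The 31% and 6% should serve as context only, since prior treatment, dose levels and the evaluable set differ from those studies.

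Optionally, in section 13.5, stratify or adjust the marker analyses for tumor type and name the test. A small-sample method is preferable because responders will be few: with no AR-42 effect and 25% to 75% RCC, about 29 × 0.1225 = 3.6 to 35 × 0.2475 = 8.7 are expected, fewer if the RCC rate is lower. In simulations with tumor type included (1,500 trials per cell), Firth regression held the false-positive rate at 3.3-4.9% and a permutation test within tumor type at 4.3-5.3%. The choice is the biostatistician's.

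**Cost.** No new data, patients or endpoints are needed. Intervals within each disease will be wide, and wider if the mix is uneven: at 8 RCC and 24 STS, 2/8 gives 3.2-65.1% and 1/24 gives 0.1-21.1%. Marker power falls slightly. For an odds ratio of 2 per SD at 16:16 it is 28.5% unadjusted (likelihood ratio), 24.3% with Firth and 26.2% with permutation; for an odds ratio of 3 it is 52.5%, 50.1% and 52.1%. The split does not address the variety of histologies within STS.
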